5.2.3 Progression-Free Survival (PFS)

PFS is defined as the time from the date of first dose until the date of disease progression as assessed by modified RECIST 1.1, or until death due to any cause. If a subject has neither progressed nor died, the subject will be censored at the date of last disease assessment or at the date of registration if no post-baseline radiological assessment is available. Subjects who receive any further anticancer therapy for the disease before disease progression will be censored at the date of the last disease assessment before the anticancer therapy started. If progression or death occurs after missing 2 scheduled disease assessments, the subject will be censored at the date of last disease assessment or at the date of registration if no post-baseline disease assessment is available. A subject has missed 2 scheduled disease assessments if the gap between two disease assessments is more than 2.5 times the scheduled disease assessment interval. During treatment, this will be 105 days (2.5 x 42 days during treatment for the first 24 weeks); during the follow-up period this will be 210 days (2.5 x 84 days during follow-up).

PFS (in days) is calculated as:

(Date of death, or Progression assessed by modified RECIST 1.1, or censoring) – (Date of first dose) +1.

To apply the cut-off date to PFS is to exclude disease assessments, death and anti-cancer therapy date after cut-off date in the analysis.

Note: Patient cannot be censored at “Not Evaluable (NE)”. If NE is the only previous assessment, then PFS will be censored at Day 1.

PFS will be calculated for each subject using RECIST 1.1 alone, and serum markers alone.

Table 3 PFS Definition

Situation	Date of Event or Censor	Outcome
No evaluable post-baseline efficacy assessments, no death	Date of first dose	Censor
Subject did not receive new anti-cancer therapy:		
Disease progression documented per modified RECIST v1.1	Date of PD	Event
No disease progression, but death recorded on eCRF	Date of death	Event
No PD nor death	Date of last efficacy assessment or at the date of first dose if no postbaseline efficacy assessment is available	Censor
Subject received new anti-cancer (ACT) therapy:		
Disease progression documented per modified RECIST v1.1 after new ACT	Date of last efficacy assessment before start of new anti-cancer therapy or at the date of first dose if no post-baseline efficacy assessment is available	Censor
Disease progression documented per modified RECIST v1.1 before new ACT	Date of PD	Event
No disease progression before new ACT but death recorded	Date of last efficacy assessment before start of new anti-cancer therapy or at the date of first dose if no post-baseline radiological assessment is available	Censor
No disease progression nor death	Date of last efficacy assessment before start of new anti-cancer therapy or at the date of first dose if no post-baseline efficacy assessment is available	Censor
Missed 2 scheduled efficacy assessments:		
If disease progression or death occurs after missing 2 scheduled efficacy assessments	Date of last efficacy assessment or at the date of first dose if no postbaseline efficacy assessment is available	Censor

PFS = Date of Event or Censor – Date of First Dose +1

PFS by RECIST1.1 will be also be derived as described in [Table 3](#).

5.3 Safety Endpoints

Safety endpoints such as DLTs, AEs, laboratory tests, vital signs, ECGs and ECOG performance status are secondary endpoints of the study.

Safety will be assessed by evaluation of the following variables:

5.3.1 Adverse Events

5.3.1.1 Dose-Limiting Toxicities

DLT criteria are defined in section 2.2.1.1.

5.3.1.2 Treatment-Emergent Adverse Events

Treatment-emergent adverse events (TEAEs; frequency, severity, seriousness, and relationship to study drug).

TEAE is defined as an adverse event observed after starting administration of the study drug, and up to 30 days after the last dose of study drug. If the adverse event occurs on Day 1 and the onset check box is marked “Onset after first dose of study drug” or the onset check box is left blank, then the adverse event will be considered treatment-emergent. If the adverse event occurs on Day 1 and the onset check box is marked “Onset before first dose of study drug”, then the adverse event will not be considered treatment-emergent. If a subject experiences an event both during the preinvestigational period and during the investigational period, the event will be considered as TEAE only if it has worsened in severity (i.e. it is reported with a new start date). All adverse events collected that begin within 30 days after taking the last dose of study drug will also be counted as TEAE. Any AEs with onset dates completely missing will be considered TEAEs in summaries. AEs with partially missing onset dates will be assumed TEAEs unless the available portion of the date indicates that the onset was strictly before start of study medication.

A drug-related TEAE is defined as any TEAE with at least possible relationship (possibly or probably related) to study treatment as assessed by the investigator or with missing assessment of the causal relationship

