5.5 Adverse Events and Other Safety Aspects

5.5.1 Definition of Adverse Events

An AE is any untoward medical occurrence in a subject administered a study drug, and that does not necessarily have to have a causal relationship with this treatment. An AE can therefore be any unfavorable and unintended sign (including an abnormal laboratory finding), symptom, or disease (new or exacerbated) temporally associated with the use of a medicinal product whether or not considered related to the medicinal product.

In order to identify any events that may be associated with study procedures and could lead to a change in the conduct of the study, Astellas collects AEs even if the subject has not received study drug treatment. AE collection begins after the signing of the informed consent and will be collected until 30 days after the last dose of study drug or the subject is determined to be a screen failure.

Care will be taken not to introduce bias when detecting AEs and/or serious adverse events (SAEs). Open-ended and non-leading verbal questioning of the subject is the preferred method to inquire about AE occurrences.

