7.10 Handling of Missing Data, Outliers, Visit Windows, and Other Information

As a general principle, no imputation of missing data will be done. Exceptions are the start and stop dates of AEs and concomitant medication. The imputed dates will be used to determine whether or not an AE is treatment emergent and the medication is concomitant. Listings of the AEs and concomitant medications will present the actual partial dates; imputed dates will not be shown.

See the SAP for details of the definitions for windows to be used for analyses by visit.

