2.2 Study Design

This is a phase 2, open-label, single-arm, multicenter study to assess the safety and efficacy of ASP1650, an mAb targeting CLDN6, in male subjects with incurable platinum refractory germ cell tumors. Up to 46 subjects at approximately 3 centers located in the United States will participate in the study.

The study consists of 2 phases: Safety Lead-in phase and phase 2. For all subjects, the study will consist of the following periods: Screening, Enrollment, Treatment and Follow-up. Each subject may complete a maximum of 12 treatment cycles. One treatment cycle is 14 days. After discontinuation of study drug treatment, all subjects will complete a study treatment discontinuation visit and a safety Follow-up visit.

1. Screening and Enrollment Period

Screening will take place up to 45 days prior to enrollment. Re-screening may be allowed 1 time per subject upon discussion with the medical monitor.

2. Treatment Period

Safety Lead-in Phase

The Safety Lead-in phase of this study is to establish the tolerability of RP2D (ASP1650 1500 mg/m² once every 2 weeks [Q2W]). An initial dose level of ASP1650 1000 mg/m² Q2W will be evaluated in a 3-subject cohort (cohort 1), and if well tolerated, a new subject cohort (minimum 3 and up to 4 subjects) will be opened to evaluate a dose level of ASP1650 1500 mg/m² Q2W (cohort 2) according to the Bayesian Optimal Interval (BOIN) Design. [Liu et al, 2015]. Based on tolerability observed in cohort 2, an additional subject cohort (cohort 3) will be opened to evaluate 1500 mg/m² Q2W (minimum 3 and up to 4 subjects) or de-escalation to 1250 mg/m² Q2W if 1500 mg/m² Q2W is not tolerable (minimum 6 and up to 8 subjects). Nine to 18 subjects will be enrolled in the Safety Lead-in phase. The RP2D determination will be based on at least 6 evaluable subjects at the RP2D as determined by the Dose Evaluation Committee (DEC).

There will be at least 3 calendar days between the treatment initiation of the first subject and treatment initiation of all subsequent subjects at the same dose level.

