6.11 Additional Conventions

6.11.1 Missing Data

Every effort will be made to resolve missing or incomplete dates for adverse events, concomitant medications, anti-cancer therapy, and death. If a partial date cannot be resolved, the most conservative imputation methods will be used to complete the missing information.

Missing or partial start and stop dates of adverse events and concomitant medication will be imputed using the following algorithm:

- Imputation rules for partial or missing stop dates:
 - If the month and year are present, then impute as the last day of that month.
 - If only the year is present, impute as December 31 of that year.
 - If the stop date is entirely missing, assume the event or medication is ongoing.

Imputation rules for partial or missing start dates:

Start Date		Stop Date				Partial: yyyy		Missing
		Complete: yyyymmdd		Partial: yyyymm		< 1 st dose	≥ 1 st dose	
		< 1 st dose	≥ 1 st dose	< 1 st dose yyyymm	≥ 1 st dose yyyymm	< 1 st dose yyyy	≥ 1 st dose yyyy	
Partial: yyyymm	= 1 st dose yyyymm	2	1	2	1	n/a	1	1
	≠ 1 st dose yyyymm		2		2	2	2	2
Partial: yyyy	= 1 st dose yyyy	3	1	3	1	n/a	1	1
	≠ 1 st dose yyyy		3		3	3	3	3
Missing		4	1	4	1	4	1	1

1 = Impute as the date of first dose; 2 = Impute as the first of the month; 3 = Impute as January 1 of the year; 4 = Impute as January 1 of the stop year

The imputed dates will be used to determine whether an AE is/is not treatment emergent. Listings of AEs and concomitant medications will present the actual partial dates; imputed dates will not be shown.

For secondary endpoint PFS or DOR, missing or incomplete death date will be imputed as the earliest feasible date on or after the date last known to be alive as the examples shown in the table below.

Incomplete Date of Death (YYYY MMM DD)	Date Last Know to be Alive (YYYY MMM DD)	Imputed Date of Death (YYYY MMM DD)
2005 APR ??	2005 MAR 31	2005 APR 01
2005 ??? 13	2005 MAR 31	2005 APR 13
2005 ??? ??	2005 MAR 31	2005 MAR 31
???? APR ??	2005 MAR 31	2005 APR 01
???? APR 13	2005 MAR 31	2005 APR 13
???? ??? ??	2005 MAR 31	2005 MAR 31

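### SAP 5.3.1.2 flags some adverse events that ended before the first dose as treatment-emergent, while SAP 6.11.1 and protocol 7.10 make the same records not treatment-emergent (minor)

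*SAP*

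**What the plan says.** Two sections of the SAP decide TEAE status when the onset date is incomplete.

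- **SAP 5.3.1.2** defines a TEAE as an event seen after study drug has been started, up to 30 days after the last dose. It then adds two rules for incomplete onset. For no date at all: "Any AEs with onset dates completely missing will be considered TEAEs in summaries". For a partial date: "AEs with partially missing onset dates will be assumed TEAEs unless the available portion of the date indicates that the onset was strictly before" the start of study medication. Neither rule looks at the stop date.
- **SAP 6.11.1** imputes the start date from a table that crosses what is known of the start with whether the stop falls before, or on or after, the first dose. With a pre-dose stop, a missing start gets code 4: "4 = Impute as January 1 of the stop year". A start known only to the month or year of first dose gets code 2 or 3: "2 = Impute as the first of the month; 3 = Impute as January 1 of the year". The section then states: "The imputed dates will be used to determine whether an AE is/is not treatment emergent".

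Protocol 7.10 agrees with SAP 6.11.1: "The imputed dates will be used to determine whether or not an AE is treatment emergent". Neither document says which rule takes precedence.

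**The concern.** The same record can be a TEAE under one section and not under the other. Two programmers who each follow the SAP could therefore produce different TEAE tables.

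Such records can exist. Protocol 5.5.1 says "AE collection begins after the signing of the informed consent", and SAP 2.2 says "Screening will take place up to 45 days prior to enrollment". An event can begin and resolve in that window and be recorded with a usable stop date but an incomplete onset.

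At stake is the accuracy of TEAE tables with small denominators. SAP 6.5.2 also tabulates non-serious TEAEs that reach 5% in any treatment group. One subject reaches that threshold in any group of 20 or fewer (1/20 = 5%).

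**Working it through.** **Inputs.** The two onset rules in SAP 5.3.1.2; the start-date table and codes 1 to 4 in SAP 6.11.1; the sentences in SAP 6.11.1 and protocol 7.10 that make the imputed date decisive. The plan gives no figure to reproduce.

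**Step 1: what 6.11.1 gives when the stop precedes the first dose.** With internally consistent dates, codes 2, 3 and 4 each place the start at the beginning of a month or year that is no later than the stop. Hence imputed start ≤ stop < first dose, and the event is not a TEAE.

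**Step 2: the two rules side by side, pre-dose stop.**

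| Onset recorded as | SAP 5.3.1.2 | SAP 6.11.1 | Conflict |
|---|---|---|---|
| Completely missing | TEAE | Code 4, not TEAE | Yes |
| Month of first dose, day unknown | TEAE | Code 2, not TEAE | Yes |
| Year of first dose, month unknown | TEAE | Code 3, not TEAE | Yes |
| Earlier month, or earlier year only | Not TEAE | Code 2 or 3, not TEAE | No |

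**Step 3: examples.**
- First dose 15 June 2020, onset missing, stop 10 June 2020. 5.3.1.2 gives TEAE. 6.11.1 imputes 1 January 2020, so not TEAE.
- First dose 20 May, onset May (day unknown), stop 10 May. 5.3.1.2 gives TEAE. 6.11.1 imputes 1 May, so not TEAE.
- First dose 20 May, onset April (day unknown), stop 10 May. Both give not TEAE.

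**Step 4: enumeration.** Both rules were applied to 730 first-dose dates, true onsets from day −45 to day +57 in steps of 3 days, and durations of 0, 5, 20 and 40 days, with complete stop dates. With the stop before the first dose, the flags differed in:
- 29,200 of 29,200 cases with onset missing;
- 26,998 of 29,200 cases with year only;
- 6,506 of 29,200 cases with year and month.

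In the remaining 2,202 year-only and 22,694 year-month cases, both rules gave not TEAE. With the stop on or after the first dose there were no conflicts. These counts show where the conflict lies; they are not expected frequencies.

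**Step 5: largest effect on one table row.** One subject is 1/3 = 33% in a 3-subject cohort, 1/8 = 12.5% to 1/6 = 16.7% at the 6–8 subjects planned for 1500 mg/m² in the lead-in, and 1/34 = 2.9% in a 34-subject phase 2 group.

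**The case against.** The best defence is that the documents already point to one answer. The opening definition in 5.3.1.2 excludes an event that ended before exposure, so its two missing-date sentences can be read as conservative defaults for undetermined cases. SAP 6.11.1 gives a full algorithm, and protocol 7.10 supports it. This shows which rule ought to prevail, and it stands to that extent. It does not remove the problem: the sentence on completely missing onset has no exception, and no text ranks the two sections.

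The trigger is also narrow. The event must start after consent, resolve before the first dose, have a stop date good enough to show this, and have an onset that is missing or known only to the first-dose month or year. SAP 6.11.1 also commits to resolving incomplete dates where possible. All of this stands and keeps the point minor.

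Three stronger readings are tempting, and the documents do not support them.
- A reader might infer that every partial onset with a pre-dose stop is misflagged. Partial onsets in an earlier month or year are excluded by both sections.
- A reader might infer that screening events are thereby attributed to the drug. TEAE status concerns timing. Under SAP 5.3.1.2, such an event enters the drug-related tables only if the investigator's causality assessment is related or is missing.
- A reader might take 33% as the expected distortion. SAP 6.5.2 counts subjects once per preferred term and once per body system, so a row changes only if that subject has no other qualifying TEAE in it.

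**Conclusion.** SAP 5.3.1.2 is wrong as written, and the error is minor. For an event with a recorded stop before the first dose, it conflicts with SAP 6.11.1 and protocol 7.10 when the onset is completely missing or is known only to the month or year of first dose. Of the two rules, 5.3.1.2 is the one to change, because its result contradicts its own definition of a TEAE.

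The percentages in the working are upper bounds for a single row and assume one affected subject. The documents give no frequency for such records. That they will be few is a judgement; that they can occur follows from AE collection starting at consent.

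The consequence stays within the TEAE tables. The primary response endpoint does not use this flag. Nor is there ground to infer an effect on dose decisions, since under protocol 2.2.1 the Dose Evaluation Committee reviews individual subject safety data.

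**What to change.** Either change to SAP 5.3.1.2 is enough.

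1. Add to both missing-date sentences: *unless the complete or partial stop date shows the event ended before the first dose*. Partial stop dates need naming because the table in 6.11.1 classifies them too.
2. Replace both sentences with: *TEAE status is determined from the dates imputed in 6.11.1*. Records imputed to the first-dose date (code 1) then fall under the existing Day 1 rule and remain TEAEs if the onset check box is blank or marked as after the first dose. A record whose box is marked as before the first dose would not be a TEAE.

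The second option leaves a single rule and matches protocol 7.10. Either costs one SAP sentence, with no change to data collection, sample size or the protocol, and should be settled before database hard lock.

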5.3.1.3 Serious Adverse Events

Serious Adverse Events (SAEs) include adverse events that are flagged as serious by the investigator on eCRF, or upgraded by the Sponsor based on review of the Sponsor’s list of Always Serious term.

5.3.1.4 Clinical Laboratory Variables

Below is a table of the laboratory tests that will be performed during the conduct of the study.

Additional laboratory tests should be performed according to institutional standard of care. Clinical significance of out-of-range laboratory findings is to be determined and documented by the investigator or delegated sub-investigator who is a qualified physician.

Table 4 Laboratory Assessments

Panel/Assessment	Parameters to be Analyzed	NCI-CTCAE Grading (Hyper/Hypo)
Hematology	Hematocrit (Hct) Hemoglobin (Hgb) Red Blood Cell Count (RBC) White Blood Cell Count (WBC) WBC differential Absolute Neutrophil Count (ANC) Platelets Mean Corpuscular Volume (MCV) Mean Corpuscular Hemoglobin (MCH) Mean Corpuscular Hemoglobin Concentration (MCHC)	N/A Both N/A Both Both Hypo Hypo N/A N/A N/A
Biochemistry	Albumin Blood Urea Nitrogen (BUN) Calcium Bicarbonate Chloride Creatinine Estimated glomerular filtration rate Glucose Magnesium Phosphate Potassium Sodium Total Bilirubin Total Protein Alanine Aminotransferase (ALT) Alkaline Phosphatase (ALP) Aspartate Aminotransferase (AST) Amylase Lipase	Hypo N/A Both Hypo N/A Hyper N/A Hypo Both N/A Both Both Hyper NA Hyper Hyper Hyper Hyper Hyper
Table continued on next page		

Panel/Assessment	Parameters to be Analyzed	NCI-CTCAE Grading (Hyper/Hypo)
Urinalysis	Color Clarity/turbidity pH Specific gravity Glucose Ketones Nitrites Leukocyte esterase Bilirubin Urobilinogen Blood Protein Microscopic urinalysis to be performed if abnormal dipstick	N/A N/A N/A N/A N/A N/A N/A N/A N/A N/A N/A N/A N/A
Grade 3 or 4 IRR	Cytokine/Chemokine Panel*	N/A
Any reaction with features of anaphylaxis	Serum Total Tryptase*	N/A
Biomarkers	Alpha-fetoprotein (AFP) Beta human chorionic gonadotropin (βhCG)	N/A N/A
Coagulation	Prothrombin time (PT) (sec) Partial Thromboplastin Time (PTT) International normalized ratio (INR)	Hyper Hyper Hyper
Thyroid Function Test	Thyroid stimulating hormone (TSH) Free T4 (thyroxine)	N/A N/A

5.3.1.5 Vital signs

Vital signs include systolic and diastolic blood pressures (mmHg), radial pulse rate (beats/minute) and body temperature (degrees Celsius).

5.3.1.6 Other

- 12-lead electrocardiogram (ECG)
- ECOG performance scores
- Body Mass Index (BMI)

$$\text{BMI} = \text{weight (kg)} / [\text{height (m)}]^2$$

- Duration of exposure

Duration of exposure to a study drug will be calculated in days, using the following formula:

(Date of last dose of study drug – Date of first dose) + 1

When the start or stop date is missing, for example if the subject is ongoing, then the exposure will be treated as missing.

- Cumulative Actual Dose

Total amount of study drug actually taken by the patient from first dose date to last dose date

- Planned Dose Intensity

Planned dose intensity for ASP1650 is 1000 mg/m² Q2W or 1500 mg/m² Q2W.

- Actual Dose Intensity

Defined as the cumulative actual dose in mg divided by duration of exposure in days.

- Relative Dose Intensity (RDI)

Actual Dose Intensity

----- x 100

Planned Dose Intensity

- Previous and concomitant medication

- Previous medication is defined as medication with at least one dose taken before the date of the first dose of study drug.
- Concomitant medication is defined as medication with at least one dose taken between the date of first dose (inclusive) and the date of last dose (inclusive) of study drug.

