5.1.5 Criteria for Continuation of Treatment

Subjects will be treated with ASP1650 on day 1 of each cycle (each cycle has 14 days). All subjects will be treated for a maximum of 12 cycles or until the subject meets study treatment discontinuation criteria. ASP1650 will not be made available after conclusion of the study to subjects who are still receiving and benefiting from study treatment.

In case of premature study termination, ASP1650 may be made available to subjects who are still receiving study treatment, have not yet completed 12 cycles of treatment and who are still benefiting from study treatment until study defined treatment discontinuation criteria is met.

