Enrollment of 3 subjects at the target RP2D (1500 mg/m² Q2W) will begin once the 1000 mg/m² Q2W dose level has been deemed tolerable. A de-escalation dose cohort will be opened at 1250 mg/m² Q2W if 1500 mg/m² Q2W has been deemed not tolerable. Subjects enrolled in the 1000 mg/m² Q2W dose level will continue treatment at that dose level (unless they meet study treatment discontinuation criteria) and will be dose escalated to the RP2D after the RP2D is deemed tolerable.

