6.3 Study Drug

Summaries of drug exposure and relative dose intensity (RDI) by dose level and overall will be presented using each subject's assigned dose at treatment start.

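### The SAP's relative dose intensity rules misreport subjects dosed exactly to plan, and its exposure rule discards recorded doses for anyone still on drug

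*SAP*

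**What the plan says.** SAP 5.3.1.6 sets out the exposure variables:

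- Duration of exposure: "Date of last dose of study drug – Date of first dose) + 1".
- Subjects still on drug: "When the start or stop date is missing, for example if the subject is ongoing, then the exposure will be treated as missing".
- Actual dose intensity: "Defined as the cumulative actual dose in mg divided by duration of exposure in days".
- Planned dose intensity: "Planned dose intensity for ASP1650 is 1000 mg/m² Q2W or 1500 mg/m² Q2W".
- RDI: actual over planned intensity, times 100.

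SAP 6.3 presents exposure and RDI by dose level using each subject's "assigned dose at treatment start". SAP 6.3.2 limits RDI to subjects whose total dose and first and last treatment days are known. Its categories are <50, 50–<75, 75–<90, 90–≤100, >100 and Unknown.

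The design in SAP 2.2 has more dose paths than these rules cover. One is conditional: "A de-escalation dose cohort will be opened at 1250 mg/m² Q2W if 1500 mg/m² Q2W has been deemed not tolerable". The other is planned: subjects who start at 1000 mg/m² "will be dose escalated to the RP2D after the RP2D is deemed tolerable". Protocol 2.2.1 agrees on that second path, but Protocol 5.1.2.1 names 1500 mg/m² as the target.

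Protocol 5.1.4 has the dose recorded at every cycle. Protocol 5.1.5 caps treatment at 12 cycles but adds that, if the study stops early, "ASP1650 may be made available to subjects who are still receiving study treatment".

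**The concern.** RDI should show whether subjects received the dose the plan gave them. A subject treated exactly as planned should read 100%. Under these definitions he generally does not, for three separate reasons: some assigned doses have no planned intensity of their own, the duration stops on the day of the last dose, and numerator and denominator are in different units.

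The rule for ongoing subjects is a fourth, separate matter. The doses are recorded, so nothing about exposure up to a data cut is unknown. SAP 5.2.2 and 5.2.3 give data cut-off rules for DOR and PFS; nothing similar is given for exposure.

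At stake is whether the exposure and RDI tables can be read. A planned escalation would look like over-dosing, and real under-dosing could sit in the 90–≤100 class.

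**Working it through.** Neither document states an exposure or RDI figure, so there is none to reproduce. The check applies the SAP formulas to subjects dosed on schedule.

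**Inputs.** Cycle length is 14 days and the maximum is 12 cycles (SAP 2.2). Duration, actual and planned intensity come from SAP 5.3.1.6, and the RDI categories from SAP 6.3.2. Cohort 1 has 3 subjects (SAP 2.2).

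**Units.** Read literally, actual intensity is in mg per day and planned intensity in mg/m² per 14 days. Body surface area is not given, so assume 1.7 to 2.1 m². Twelve doses of 1500 mg/m² over 155 days then give 100 × (12 × 1500 × 1.7 / 155) / 1500 = 13.2% at the low end and 16.3% at the high end. No programmer would keep this result, but the SAP does not say how to convert. Everything below uses mg/m² per day on both sides.

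**Duration.** For n on-schedule doses the SAP duration is 14(n − 1) + 1 = 14n − 13 days. Twelve doses give 155 days, against 168 for 12 full cycles. RDI is therefore inflated by 14n / (14n − 13). A fully compliant subject measured against his own dose reads:

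| Doses | SAP duration (days) | RDI |
|---|---|---|
| 1 | 1 | 1400% |
| 3 | 29 | 144.8% |
| 6 | 71 | 118.3% |
| 12 | 155 | 108.4% |

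All fall in >100, including subjects at 1500 mg/m², for whom a planned intensity does exist. The inflation also hides shortfalls. At 12 doses, a full-interval RDI of 83.0% reads 83.0 × 168/155 = 90%; at 6 doses, 76.1% reads 76.1 × 84/71 = 90%.

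**Cohort 1 escalation.** Illustrate with 5 cycles at 1000 and 7 at 1500 mg/m²; the actual switch cycle is not in the documents. Total = 5 × 1000 + 7 × 1500 = 15,500 mg/m². Against the starting dose:

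- SAP duration: (15,500/155) / (1000/14) = 140.0%.
- Full intervals: (15,500/168) / (1000/14) = 129.2%.

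Both are >100. Other switch points behave the same way over 12 doses: 144.5% (133.3% on full intervals) after 4 doses, and 126.5% (116.7%) after 8.

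**1250 mg/m² cohort, 12 doses.** Total = 15,000 mg/m². No planned intensity is given, so the result depends on which of the two listed values is borrowed:

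| Planned intensity used | SAP duration | Full intervals |
|---|---|---|
| 1000 mg/m² | 135.5% (>100) | 125.0% (>100) |
| 1500 mg/m² | 90.3% (90–≤100) | 83.3% (75–<90) |

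One compliant subject can land in three different classes.

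**Ongoing subjects.** Take an assumed cut with 10 stopped subjects averaging 41.6 days (total 416). If 3 more are ongoing at 99, 127 and 141 days, the mean over all 13 is (416 + 367)/13 = 60.2, and the reported 41.6 is too low. If the 3 are at 15, 29 and 43 days, it is (416 + 87)/13 = 38.7, and 41.6 is slightly too high.

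**When subjects could be ongoing.** On schedule, dose 12 falls on day 155. The futility look for the 13th subject is at about day 24 × 7 + 1 = 169. Only a subject with more than 14 days of accumulated delay would still be short of dose 12. Protocol 5.1.2.2 permits such delays.

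**The case against.** The strongest reply is that little of this reaches the final report. Treatment stops at 12 cycles and the study ends at the last participant's last visit (Protocol 9), so nobody should be on drug at a normal final lock. The futility look is defined by a response count (SAP 6.10), and no exposure table is planned there. The 1250 mg/m² cohort opens only if 1500 mg/m² is not tolerable, and the documents do not say that it opened. Escalation concerns at most 3 subjects, and only those still on treatment. SAP 6.3 can also be read as a rule for table columns, not for the denominator.

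Much of this stands, and it rules out two stronger readings. A reader might infer that reported mean exposure is bound to be too low because the longest-treated subjects are dropped. The documents do not support that: a subject with 12 doses has finished and has a known last dose, and those ongoing at a cut may be recent entrants. A reader might also infer that the missing rule misclassifies subjects on RDI. It does not; SAP 6.3.2 leaves them out or calls them Unknown.

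The reply does not remove the RDI fault. If SAP 6.3 only groups columns, the SAP does not say which planned value an escalated subject gets. Against 1500 mg/m² the 5-plus-7 subject reads 140.0 × 1000/1500 = 93.3% (86.1% on full intervals), which is not his own plan either. The omitted interval and the unit mismatch affect every dose level whatever happened in the lead-in. For ongoing subjects, a lock after early termination with continued dosing remains possible under Protocol 5.1.5.

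**Conclusion.** The RDI definition should be corrected. With units aligned, a compliant 12-dose subject at 1500 mg/m² reads 108.4%, and the excess grows as the number of doses falls. An escalated cohort 1 subject reads 140% in the example used (129% on full intervals). A 1250 mg/m² cohort would have no denominator of its own.

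The rule for ongoing subjects is a lesser fault. It discards recorded doses at any cut with subjects on drug, its direction is not predictable, and its effect is nil once all have stopped.

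The results assume on-schedule dosing; the cohort 1 figure also rests on the chosen switch cycle. A reader might infer that all 34 phase 2 subjects would be misclassified through the 1250 mg/m² gap. That would need 1250 mg/m² to have become the RP2D, which the documents do not show.

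The consequence is confined to descriptive exposure and RDI tables. The ORR test does not use these variables, and the adverse event tables in SAP 6.5.2 are subject counts and percentages, not exposure-adjusted rates. This is a low-severity point that is cheap to put right.

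**What to change.** Amend SAP 5.3.1.6, 6.3 and 6.3.2 as follows.

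1. **Ongoing subjects.** Use the last recorded dose on or before the data cut-off as the stop date for duration, cumulative dose and RDI, and flag these subjects as ongoing.
2. **Actual intensity for RDI.** Divide cumulative mg/m² by (last dose date − first dose date + 14) days and express it per 14 days, so that the interval after the last dose counts.
3. **Planned intensity.** Sum, over initiated cycles, the dose level the protocol assigned to that subject at that cycle (1000, 1250 or 1500 mg/m², with the planned cohort 1 escalation from the cycle it applies). Divide by 14 × number of those cycles and express it per 14 days. Reductions for adverse events stay measured against the assigned level.
4. **Escalation target.** Reconcile Protocol 5.1.2.1, which names 1500 mg/m², with Protocol 2.2.1 and SAP 2.2, which name the RP2D. The planned dose for cohort 1 depends on this.

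Check: the 5-plus-7 subject on schedule then has 15,500/168 on both sides, so RDI = 100%. With 14 days of total delay he reads 168/182 = 92.3%, so delays still lower RDI.

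The cost is SAP wording and minor programming; the doses and dates needed are already collected.
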